Intervention and control groups						
Self-report measures*	X		X		X	X
Physiologic measures**	X				X	
Fall rates (mail-in)	X	X	X	X	X	X
Notes: Self-report measures* : Fall Prevention Patient Engagement Scale, Fall Efficacy Scale International, Fall Behavioral Scale, Patient Activation Measure. Physiologic measures** : Timed Up and Go, 30-Seconds Sit-to-Stand, & 4-Stage Balance Test. E : Documented in study encounter notes (narrative descriptions of behavior change topic, behavioral goal, readiness to change, importance, confidence, commitment, barriers & facilitators for change, change from the last study encounter, satisfaction).						
wk : week, m : month						
⁺ : Visits: includes 3 options: in-home (virtual and in-person) & study office in-person visits						

Study population

Number of subjects. We estimated the sample size based on the key primary outcome measure, fear of falling as measured by FES-I, which has a reported effect size ranging from .03 to .42 depending on the setting and the type of intervention. The PI's MI intervention with inpatients found an effect size of .31 with high fall-risk inpatients. Using the power of 80% and alpha of 0.05, we need a minimum of 120 participants for an independent t-test calculation. To account for attrition, we aim to enroll 250 participants.

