Study measurements. Several standardized study tools will be used at baseline, 3-months, 6-months, and 12-months after the benchmark STEADI clinic visit. The study domains and measurement tools are summarized in Table 2. The primary study outcome measures are: patient engagement with fall prevention recommendations (medication, exercise, blood pressure, vision, and environment), fear of falling, and fall prevention behaviors. The study will create, pilot test, and use the Fall Prevention Patient Engagement Scale created for the study to measure frequency and uptake of STEADI recommendations. Falls Self-Efficacy Scale-International (FES-I), a 16-item scale, is widely used to measure levels of concern related to preventing falls. Higher FES-I scores have been positively correlated with decreased activities, future falls, and injury. The 24-item version of Fall Behavioral Scale (FAB), will be used to capture patients' daily activities to prevent falling. FAB measures frequency of protective strategies to prevent falling and risky behaviors that facilitate a fall. Secondary study measures include physical function, patient activation, and fall rates. All participants will mail-in monthly fall calendar, the gold standard to capture fall rates. The chart reviews will be used to capture health status and other patient data.

[COVID-related change]

We will add a modified recruitment approach, to recruit patients who had the STEADI FRA/clinic visit up to a year ago. This clinic visit is when participants receive fall risk assessment and fall prevention recommendations. Since the duration between the time that they receive fall prevention recommendations and the initiation of the study could vary as much as a year, 1) we will add questions to assess what changes have taken place related to fall prevention since the clinic visit within Fall Prevention Patient Engagement Scale: pre-enrollment), 2) we will review STEADI recommendations at the baseline visit with all participants to refresh participants' memory on clinic recommendations, and 3) we will analyze the impact of the length of time between the STEADI clinic visit and study outcomes.

We propose to have multiple options available for baseline and 6-month study visits in addition to in-person study office visits as originally planned. This will allow for flexibility in participants' involvement with the study. We will have options for at-home virtual (phone or video) and in-person visits.

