With the inclusion of virtual encounters, a visit may be divided up into multiple sessions due to unexpected internet or living situations. For example, baseline visit is expected to be conducted in 2 sessions for the control group, and 3 sessions for the intervention group. The first session will include a review of fall prevention recommendations made at the STEADI clinic visit, self-report questions (FESI, FAB, etc), instruction about the fall calendar, and processes for the physiologic measurement during the next session (equipment, support person, environment, physical condition, internet access). The second session will be for STEADI physiologic measures (30-second sit to stand, 4-stage balance test, time up and go, and orthostatic blood pressure if possible). The participants in the intervention group will have the third session for the MI intervention #1.

Once the clinic starts normal operations, we will contact patients who received STEADI FRA and recruit them into the study. The baseline visit will be conducted in 2 (control group) or 3 (intervention group) sessions as described above.

The 6-months physiologic assessment will be conducted at the same location as the baseline location.

[Responses to fall incidents during the study data collection period]

When participants report fall incidents through their fall calendar or during study visits, the study staff will follow-up on the incident. Unless participants have a planned study visit within a month, the study staff will make a brief caring call to inquire how they are doing after the fall. We will refer them to CDC resources on fall prevention and the study packet if they are interested in information, and encourage them to talk to their provider. If the study team assesses that the fall warrant healthcare or clinical intervention beyond the scope of the research, the study may contact the provider with participants' permission.

[Updates to enhance recruitment and retention]

We will send quarterly study newsletters via email and/or postal mail to all study participants to enhance their engagement with the research. We will work with IRB and OHSU Branding Department to use approved formats. Additionally, we will also send birthday cards to participants for retention. Content and final drafts of the study newsletters and birthday cards will be submitted to the IRB for approval before distribution.

[Update 1/19/23: Study evaluation interview with enrolled participants]

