Staff will wear mask and practice hand hygiene. Work hours are variable depending on the study status and the preference of the worker. It is expected to be 6-15 hours/week. The hours will not exceed 30 hours/ week.

-
- Study staff will disinfect surface touched by participant between the visits.
- If possible, windows will be open for improved ventilation.
- The study visit will be conducted one participant at a time ensuring 6-feet distance between the staff and participant except to ensure safety during physiologic assessments.

Analysis

First, we will examine the following: recruitment, retention (numbers contacted, consented, screened out, and completed 70% of the intervention), and reasons for not participating or withdrawing. We will ask participants about challenges related to participation at 3-month, 6-month, and 12-month study encounters. Second, to determine the primary impact of MI as compared to a standard care group, patients' engagement with fall prevention recommendations (medication, exercise, blood pressure, vision, and environment), fear of falling, and fall prevention behaviors will be assessed quantitatively. The secondary impact will be measured by physical functions, patient activation, and fall rates. Descriptive statistics will be used to identify distributions and frequencies of the study outcomes. Third, we will use qualitative approach to determine how MI engages individuals in fall prevention behaviors. We will use quantitative findings to purposefully select the sample for the qualitative analysis. We will review the transcribed MI sessions and analyze the findings.

[COVID-related changes]

We will conduct additional analyses to evaluate 1) how the time between the STEADI FRA and the baseline study visit influence the recall of the FRA recommendations, engagement with fall prevention activities, and engagement with the study, 2) the difference in study outcomes between virtual vs. in-person visits, and 3) the impact of COVID-19 on fall prevention.

Privacy, confidentiality, and data security

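### Apart from a t-test used to size FES-I, the plan names no between-arm analysis for its three primary outcomes; a baseline-adjusted comparison with a defined time point can be specified from data already planned

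*Combined protocol and SAP*

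**What the plan says.** The Analysis section sets out to determine the effect of MI against standard care. It says that patients' engagement, "fear of falling, and fall prevention behaviors will be assessed quantitatively". The only technique named there is descriptive: "Descriptive statistics will be used to identify distributions and frequencies of the study outcomes". The COVID-related additions to that section list further questions but no method.

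The Number of subjects paragraph sizes the trial on FES-I: "we need a minimum of 120 participants for an independent t-test calculation". It cites a range of effect sizes from .03 to .42 and adds that the team's own "MI intervention with inpatients found an effect size of .31 with high fall-risk inpatients". It does not say how .31 was standardised, whether the test would use follow-up or change scores, or at which visit.

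The Table 1 notes list the self-report measures as "Fall Prevention Patient Engagement Scale, Fall Efficacy Scale International, Fall Behavioral Scale, Patient Activation Measure". That row covers both arms and is marked at baseline, 3, 6 and 12 months. Study measurements agrees on the visits but counts them from the clinic visit: "Several standardized study tools will be used at baseline, 3-months, 6-months, and 12-months after the benchmark STEADI clinic visit". The Control group paragraph uses the same origin.

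The COVID-related change under Study measurements allows up to a year between the clinic visit and study start. It adds baseline questions on "what changes have taken place related to fall prevention since the clinic visit within Fall Prevention Patient Engagement Scale: pre-enrollment". Self-report falls in the first baseline session, and "The participants in the intervention group will have the third session for the MI intervention #1".

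**The concern.** The trial is meant to test effectiveness, but the plan does not say how the arms will be compared. The estimate could come from follow-up, change or baseline-adjusted scores, at 3, 6 or 12 months. These choices differ in precision. If they are made after the data are seen, they also affect the error rate. The only test named ignores a baseline score that is collected anyway, so precision would be lost for nothing.

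Two further gaps make a bare mention of a visit insufficient. Visits are counted from a clinic visit that may precede study start by up to a year, so 6 months could mean different exposure to MI for different participants. The engagement scale's baseline form also has added items, and the document does not say whether its score matches the follow-up score.

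**Working it through.** **The plan's own figure.** Per arm, n = 2(1.960 + 0.842)²/d². At d = .31 this is 2 × 7.849/.0961 = 163.3, so 164 per arm or 328 in total. At d = .42 it is 89 per arm or 178 in total. The stated 120 does not follow from either. That is a separate issue, and nothing below uses 120.

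**Inputs from the document.** Alpha 0.05 (taken as two-sided); effect .31; 125 per arm planned (Randomization); 101 in the intervention arm (Appendix 2, addition of 12/30/22).

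**Assumptions not in the document.** Baseline/follow-up correlation ρ of .3, .5 or .7; .31 is a difference in raw SDs; equal variances and linearity; one outcome at one visit; everyone in the stated n evaluable. For 101, the control arm is taken as equal, since its size is not given.

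**Variance of the arm difference, relative to follow-up scores.** This does not depend on .31.

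| Analysis | Formula | ρ = .3 | ρ = .5 | ρ = .7 |
|---|---|---|---|---|
| Follow-up scores | 1 | 1 | 1 | 1 |
| Change scores | 2(1 − ρ) | 1.40 | 1.00 | .60 |
| Baseline-adjusted | 1 − ρ² | .91 | .75 | .51 |

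Adjusted over change is (1 − ρ²)/[2(1 − ρ)] = (1 + ρ)/2, which is below 1 for any ρ below 1.

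**Power.** Noncentral t with noncentrality (.31/√v)·√(n/2), where v is the entry above; the adjusted analysis loses one further degree of freedom. Example at ρ = .5 and n = 125: √62.5 = 7.906. Follow-up scores give .31 × 7.906 = 2.45, power .685. Adjusted scores give (.31/√.75) × 7.906 = 2.83, power .805.

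| n per arm | Analysis | ρ = .3 | ρ = .5 | ρ = .7 |
|---|---|---|---|---|
| 125 | Follow-up t-test | 68% | 68% | 68% |
| 125 | Change t-test | 54% | 68% | 88% |
| 125 | Adjusted | 73% | 80% | 93% |
| 125 | Gain over better t-test (points) | 4 | 12 | 4 |
| 101 | Follow-up t-test | 59% | 59% | 59% |
| 101 | Change t-test | 46% | 59% | 81% |
| 101 | Adjusted | 63% | 72% | 87% |
| 101 | Gain over better t-test (points) | 4 | 12 | 6 |

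**If .31 was standardised differently.** At 125 per arm, for ρ = .3, .5, .7:
- On the baseline-adjusted SD: adjusted 68% throughout; follow-up 64%, 56%, 41%; change 50%, 56%, 61%.
- On the SD of change: adjusted 86%, 80%, 75%; follow-up 82%, 68%, 47%; change 68% throughout.

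At 101 per arm, adjusted power is 59% under the first of these readings, and 78%, 72%, 66% under the second. Adjustment ranks highest under every reading, but it does not always reach 80%.

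**Choice of visit.** Suppose each of three visits is tested at two-sided 0.05 and the best is reported. With equicorrelated normal statistics (correlation r), the error for one outcome is 1 − ∫φ(u)[Φ((1.96 − √r·u)/√(1 − r)) − Φ((−1.96 − √r·u)/√(1 − r))]³du. This gives .136, .125 and .109 at assumed r of .3, .5 and .7.

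**The case against.** The sponsor can reply that a test is implied: the sample-size paragraph names an independent t-test for the outcome it treats as key, and the Analysis section states a comparative aim. So a reader who infers that the document contains no inferential method at all goes too far. What stands is narrower. The t-test is named for sizing, covers one of three primary outcomes, has no visit or score attached, and is not carried into the Analysis section.

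The sizes are also open to challenge. No correlation is given, .31 comes from inpatients, and 125 per arm is an enrolment target that already allows for attrition. Even 101 assumes no loss. The advantage of adjustment is algebra under equal variances and linearity, not evidence from this trial. It accounts for chance imbalance in that one score, not for imbalance generally. These limits are fair, and they make the gain modest at both ends of the ρ range.

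A reader might infer that the sponsor would choose the most favourable visit, or had already compared the arms. The document supports neither. The 12/30/22 addition says that study data, including quantitative data, were to be used to pick intervention-arm interviewees with high and low change. That shows data in use, not a comparison of arms.

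Finally, a single primary visit is not the only acceptable choice. The stated aim is longitudinal, so a prespecified average over visits or another single contrast would serve equally well.

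**Conclusion.** The point holds as a free improvement. The omission is plain from the text and needs no assumption: outside the FES-I sizing t-test, no between-arm analysis is specified for the three primary outcomes, with no baseline adjustment and no primary time point or contrast.

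The size of the benefit does rest on assumptions. Under the assumed ρ of .3 to .7 and .31 on the raw SD, adjustment adds about 4 to 12 points of power over the better t-test. It would be wrong to infer that adjustment secures 80% power: at 101 per arm on that reading it does so only at ρ = .7. The rise in error to about 11–14% applies only if the best of three visits were picked after seeing the data. Multiplicity across the three outcomes, and the derivation of 120, are separate matters.

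**What to change.** Add to the Analysis section:

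1. For each primary outcome, the arm difference with 95% CI, adjusted for the baseline score of the same scale, by ANCOVA or by a mixed model using all follow-up visits. Either is acceptable.
2. One time point named by the sponsor, or one prespecified contrast over visits.
3. The origin from which that time is counted (clinic visit, baseline visit or randomisation), reconciled across Table 1, Study measurements and Control group.
4. For the engagement scale, use of the baseline score only if the baseline form gives a score comparable with follow-up; otherwise, which baseline item is used, or that none is.
5. Confirmation that baseline self-report was collected before the arm was known. The baseline sessions place it before the first MI session, but the Randomization paragraph does not place it before allocation.
6. The date the model was fixed and what outcome data had been seen by then, given the interviewee selection in the 12/30/22 addition.

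The cost is analysis wording and routine code. No new data, visits or participants are needed.

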NCT 04612842

Engaging Older Adults in Fall Prevention Using Motivational Interviewing (MI)

Study Protocol

Oregon Health & Science University IRB #8993

PI: [name]

January 19th, 2023

One-third of older adults fall every year in the United States. Many accidental falls can be prevented through fall risk assessment and evidence-based interventions. The interventions may include advice for exercise, medication adjustment, blood pressure management, environmental modifications, and improving vision. However, older adults do not consistently follow these recommendations for a number of reasons, including their perceptions about falls and fall prevention. Emerging evidence indicates that a recommendation alone is not sufficient to engage patients in fall prevention. Yet, studies that explore alternate ways to improve patients' engagement with fall prevention are rare. Thus, we propose Motivational Interviewing (MI), an intervention known to be effective in engaging individuals in developing healthier habits, to target older adults' barriers to fall prevention.

The goal of this mixed-methods, two-arm, randomized controlled trial of MI intervention for fall prevention is to evaluate the impact of Motivational Interviewing (MI) as a follow-up care to patients who received fall prevention recommendations at Oregon Health & Science University Internal Medicine and Geriatrics Clinic provided over 12-months. Older adult participants (older than 65) who are at increased risk for falling will be enrolled into the study. Patients will be randomly assigned to two groups: MI and the standard of care group. All participants will have a baseline and 6-months study visit that will include self-report and physiologic assessment. In addition, all participants will receive study measurement phone call at 3-, and 12-months. MI will be provided via video, phone, or in-person one week after the initial visit and then monthly for 6 months. All MI sessions will be recorded and encounter notes will be completed. Purposefully selected participants' MI sessions will be transcribed for qualitative analysis.

Design

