We will use a mixed-methods randomized controlled trial to evaluate the longitudinal impact of the STEADI protocol. See Table 1. We will study STEADI patients, patients who have received STEADI RA and fall prevention recommendations at OHSU Internal Medicine and Geriatrics. We will have two-groups. The control group participants will only receive study measurements at baseline, 3-, 6-, and 12-months baseline assessment. The intervention group will receive all the same measurements as the control group, and in addition, receive MI-based communication about fall prevention at eight occasions during the 6-month period. MI is an evidence-based communication approach for various health behavior change, however, it has not been widely applied to fall prevention interventions. Our preliminary feasibility trial with inpatients has demonstrated effectiveness of MI on fall-related patient outcomes. This protocol will test the effectiveness of MI with outpatients.

Since COVID-19 pandemic occurred in March 2020, the OHSU internal medicine clinic has limited in-person patient care hours and patients are not being routinely screened for fall risks using the STEADI protocol, impacting the study implementation. As patient-care situations are unpredictable at this time, we have following modification plans to the study protocol. Major changes are listed below and described in relevant sections of this protocol.

- 1) Identification and screening of STEADI patients using healthcare records of the past year. This will be in addition to recruitment of patients who are seen at the clinic for STEADI FRA/clinic visit as originally included in this protocol.
- 2) Addition of at-home visits (video, phone, or in-person) in place of in-person study office visits.
- 3) Changes to ensure safety of study office visits once these visits are possible.
- 4) [ADDED 7/14/20] Modification to use the information sheet for participant consent.
- 5) [ADDED 7/22/20] Details about exclusion criteria.

We request modification to the protocol as we uncovered that more than half of potentially recruitable participants did not receive fall prevention recommendations, thus because ineligible for the study.

Table 1. Study overview

	Baseline	1 wk, 1 & 2 m	3 m	4 & 5 m	6 m	12 m
Study time points	T0	T1, T2, T3	T4	T5, T6	T7	T8
Study encounter type	Visit ⁺	Phone/video	Phone	Phone/video	Visit ⁺	Phone/video
Intervention group only						
MI Intervention ^E	#1	#2, 3, 4	#5	#6 & #7	#8	

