- If the incident can be considered to be not immediate, likely, or a great threat to welfare by the study staff and the PI, study staff will encourage the participant to talk to their provider. Depending on the significance of the issue, the study staff may ask for permission for the study staff to contact the provider as an effort to minimize the harm as stated in the consent. Study staff may provide information about the suicide hotline or loneliness hotline or other resources as well.
- If it is determined that the study staff should contact the provider by the PI, participants' consent to disclose the threat will be documented in the research records. In a rare occasion where the participant refuses the study staff to communicate with the provider, PI will consult the study's mentors, DSMP, or IRB appropriately.

In the case that the disclosure of research information is consented by the participant to reduce potential threat to the welfare, we will only communicate minimally necessary information so that

the participant can receive needed services or obtain appropriate consultations based on American Psychologists Association's 2002 Ethics Code (<https://www.apa.org/monitor/jan03/10ways>)

Benefits. Participants will receive transportation cost and \$15 for each of their study visits and \$5 for participating in each of 7 study phone or video calls regardless of their performance in their fall prevention behaviors, for a maximum total incentive payment of \$65(for the intervention group). The control group participant will be paid maximum of \$35. There is a chance that participant incentives may influence patients' engagement with fall prevention activities. Thus, we will remind participants at every encounter that the payment is to recognize their time to participate in the study, and their performance on fall prevention behaviors will not influence the payment. Additionally, we will evaluate the influence of study payment at the end-of-the-study feedback opportunity from participants.

The proposed study examines the impact of MI for STEADI patients. This study will identify long-term impact of the STEADI intervention, and to examine the impact on MI in fall-related patient outcomes.

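### The control-arm maximum payment of 35 dollars does not follow from the protocol's own payment rule, which gives 40 dollars on the Table 1 schedule

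*Combined protocol and SAP*

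**What the plan says.** Payment is set out in the protocol under Risks and Benefits, in the Benefits paragraph. Participants receive transportation cost, 15 dollars "for each of their study visits and" 5 dollars "for participating in each of 7 study phone or video calls". The text continues "for a maximum total incentive payment of" 65 dollars for the intervention group. The next sentence reads "The control group participant will be paid maximum of" 35 dollars. The rates are given once, for participants in general, and no section sets a different rate for controls or exempts any of their calls.

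The schedule is given elsewhere:

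- The opening overview states "All participants will have a baseline and 6-months study visit" and "all participants will receive study measurement phone call at 3-, and 12-months".
- The Design section says of controls: "The control group participants will only receive study measurements at baseline, 3-, 6-, and 12-months baseline assessment". The Control group section lists the same four time points.
- Table 1 shows baseline (T0) and 6 months (T7) as visits, 3 months (T4) as a phone contact and 12 months (T8) as phone or video. The self-report measures are collected in both arms at all four.

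**The concern.** One rule and one schedule should produce both maxima. They produce the MI figure exactly and miss the control figure by 5 dollars.

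The figure is part of the operative payment terms of an IRB protocol. The 3- and 12-month calls collect the self-report measures, which include the three primary outcomes: engagement with recommendations, fear of falling and fall prevention behaviours. If 35 dollars were enforced as a cap, the arms would be paid differently for the same outcome assessments, with the lower payment going to the arm that has fewer contacts. The Benefits paragraph itself recognises that incentives may influence engagement, and the Analysis section examines retention. An unexplained difference in payment between the arms is best avoided when it costs so little to remove.

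**Working it through.** **Inputs**

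- Rate per visit: 15 dollars (Benefits paragraph).
- Rate per call: 5 dollars, with 7 calls named (Benefits paragraph).
- Visits in both arms: 2, at baseline and 6 months (overview; Table 1, T0 and T7).
- Contacts by phone or video in the MI arm: T1, T2, T3 (1 week, 1 and 2 months), T4 (3 months), T5, T6 (4 and 5 months) and T8 (12 months), so 3 + 1 + 2 + 1 = 7 (Table 1).
- Measurement calls in the control arm: T4 and T8, so 2 (overview; Table 1).
- Planned controls: 125 (Randomization section).

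**Formula**

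Maximum = 15 x visits + 5 x calls.

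**Step 1: reproduce the MI figure.** 15 x 2 + 5 x 7 = 30 + 35 = 65 dollars, which is the stated maximum. The 7 calls in the rule match the 7 phone or video contacts in Table 1. Without either the 3-month or the 12-month call, the total on this schedule would be 15 x 2 + 5 x 6 = 60. So on the Table 1 schedule both measurement calls are among the paid calls.

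**Step 2: apply the same rule to controls.** 15 x 2 + 5 x 2 = 30 + 10 = 40 dollars. Stated: 35. Difference: 40 - 35 = 5 dollars, the price of one call.

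**Step 3: see what would give 35.**

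| Visits | Calls | Total (dollars) |
|---|---|---|
| 2 | 0 | 30 |
| 2 | 1 | 35 |
| 2 | 2 | 40 |
| 2 | 3 | 45 |
| 1 | 4 | 35 |
| 0 | 7 | 35 |

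With the two scheduled visits, only a single paid call gives 35. The other two combinations that reach 35 do not match the control schedule.

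**Step 4: rule out two side explanations.** Splitting a visit into sessions, which the COVID-related changes allow, could only raise the totals if sessions were paid separately, and the 65 dollars shows that they are not. Transportation cost is not part of the sum, because 65 is reproduced without it.

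**Step 5: size.** At planned enrolment, 125 x 5 = 625 dollars.

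**The case against.** The strongest defence is a different count of the 7 calls. The Benefits paragraph does not say which contacts they are. The Design section gives MI on eight occasions, so seven follow the baseline one, and the COVID-related change to the Intervention group section lets MI sessions be held by phone or video. If the 7 paid calls are those seven MI contacts, the MI arm gets 2 x 15 + 7 x 5 = 65. The only one that falls at a control call is the 3-month contact, so controls get 2 x 15 + 1 x 5 = 35. Both stated maxima then come out, with the 12-month call unpaid in both arms.

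This reading is possible but fits the documents less well. Table 1 places MI #8 inside the 6-month visit, and the base text of the Intervention group section treats baseline and 6 months as exceptions to phone delivery. That leaves six MI contacts by call, so the seventh call is the 12-month one. The reading also leaves the 12-month phone or video contact outside a rule that pays for study calls, without saying so. What stands is that the paragraph should name the paid calls.

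The defence is right about the limits of the point. A reader might infer that controls go unpaid for their 12-month call while MI participants are paid for theirs. The protocol does not say that any call goes unpaid, which one it would be, or in what order a cap would apply. A reader might also infer that participants were told 35 dollars. The consent form and information sheet are not in the documents, and the protocol's description of the consent form mentions only modest compensation. Nor do the documents support a claim of differential loss to follow-up: nothing in them links 5 dollars to retention, newsletters and birthday cards are planned for participants without distinction by arm, and the influence of payment is to be evaluated at the end of the study.

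**Conclusion.** The inconsistency is real and minor. The rule and the Table 1 schedule reproduce the MI maximum of 65 dollars and give controls 40 dollars against the stated 35, a shortfall of 5 dollars per control participant. The conclusion assumes that the 7 paid calls are the phone or video contacts in Table 1 and that the single stated rate applies to both arms.

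The 35 may be no more than an addition slip, with controls in fact paid 40. The documents report no payments, so they do not show that anyone was underpaid. If the figure was enforced, controls received less than the rule gives for the same assessments. Any consequence for follow-up is unquantified and probably small. The 625 dollars is a planning ceiling: it uses the planned 125 controls, and the documents do not give the number of controls actually enrolled (the later qualitative addition reports 101 allocated to the intervention arm). The sample size and the planned analysis do not depend on this figure.

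**What to change.** 1. In the Benefits paragraph, correct the control maximum from 35 to 40 dollars.
2. In the same place, name the paid calls and state that the 3- and 12-month measurement calls are paid at the same rate in both arms.
3. Check the consent form, the information sheet and any other participant-facing text, and correct the figure wherever it is repeated.
4. Check the payment records. If they show that 35 dollars was applied as a cap, pay the difference to the controls affected.

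The cost is one wording change and, only if the cap was applied, at most about 625 dollars at planned enrolment (125 x 5). No visit, outcome or analysis needs to change.
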